# 5.7 Blinding

Subjects will be blinded to the treatment group. Study staff will not be blinded to the treatment group. This is done to enable staff to respond to questions regarding the timing (i.e. on/off cycles) of the stimulation, which is treatment group specific. See 9.3 for addition discussion of blinding.

#### 6. ELITONE DEVICE

## 6.1 Device History

The ELITONE device has been evaluated clinically in prior IRB approved studies (WIRB-20162650, WIRB 20180640). See 9.1 for additional information regarding the outcomes from those studies. The product was FDA cleared in 2019 for OTC use and is commercially available. For the current study, minor software modifications have been implemented that affect the stimulation waveform and treatment regimen. In this protocol the modified configurations are referred to as ELITONE-UUI.

## 6.2 Description of Treatment Regimen

The ELITONE device delivers electrical current through an electrode component applied to the perineal region, stimulating the pelvic floor muscles and surrounding structures to improve continence. Per the product labeling, stimulation is delivered in continuous on-off cycles, 20 minutes per session, 4-5 sessions per week for 6-12 weeks. For this protocol, the treatment is more explicitly defined as detailed in Table 5-1. The design allows for convenient home-use. It comprises two main components: a disposable electrode and a controller.

Figure 6-1: Rendering of Elitone device worn on the female anatomy, under clothing.

## 6.3 Electrode Component

The electrode component is worn against the skin in the perineal region. The conductive regions are positioned such that when stimulated they deliver electrical current proximate the pelvic floor muscles. The base of the electrode is a flexible conductive ink circuit. The patient contacting elements are hydrogel and foam. Two snap connections are present on the surface facing away from the patient, which provide a connection point to a cable and the Controller component. Each electrode is provided on a removable release liner that aids in maintaining the adhesiveness and hydration of the hydrogel during use and reuse. All materials used in the electrode have histories of use in similar electrodes.

[figure not shown]

Figure 6-2: LEFT - Patient contacting side of electrode component, including conductive regions (blue) seen through the removable release liner. RIGHT - Opposite side of electrode component, including snaps for cable connection.

The electrodes are packaged in quantities of five in a resealable pouch. They are identified as part number EE-1011, and the packaging includes a lot number and Use By date. Each subject is provided with sufficient electrodes to allow use of a new electrode every other treatment session.

## 6.4 Controller Component and Accessories

The Controller component is used to supply the stimulating current. It comprises a circuit board, rechargeable battery, and user interface, all housed within a plastic housing approximately 2" x 1.5" x 0.5". The device is programmed to deliver the stimulation waveform described in 6.5. The device outputs 0-50mA (RMS) and 0-100V into a  $500\Omega$  load, which is similar to numerous commercially available electrical muscle stimulation devices and meets electrical safety standards for EMS devices (see 7.1). The output intensity is controlled by the user through a pair of increment and decrement buttons. The device can deliver at least two twenty-minute treatments on a battery charge. Recharging of the 3.7V lithium polymer battery is achieved via conventional micro-USB to USB cable. The battery includes integrated overload protection circuitry. In addition to the increment/decrement buttons, which also serve to turn on and pause/stop the device, the user interface includes a series of colored LEDs that indicate power state, and treatment intensity.

Each controller has a label that specifies the part number (EC-1003) and lot number. For the subject study, an additional label is applied that identifies the unit as "for investigational use only" and provides a unit reference number. Each subject is provided with a single controller. Accompanying the controller are additional components required for operation including the patient cable, USB charging cable, user manual, belt clip and product packaging. Note that portions of the user manual (TR-1155-FORM-12) have been modified to support blinding of the subject to her treatment group.

Figure 6-3: ELITONE Controller and all accessories, including the User Manual, Patient Cable, Charging Cable, Belt-Clip (attached to Controller) and device packaging.

#### 6.5 Stimulation Waveform

The ELITONE device outputs a two part stimulation signal, delivered at 50 Hz and 10 Hz, both modulated at 2000 Hz. The first (50 Hz) part runs for 4 seconds and the second part (10 Hz) runs for 2 seconds. It is generally understood that a 50 Hz stimulation treats SUI and a 10 Hz frequency treats UUI. After these 6 seconds of stimulation the output goes to zero for 6 additional seconds. This on/off cycling of the stimulation continues for the duration of the treatment. Intensity is set by the user, who is instructed to operate the device at a level that is maximally tolerated, but not painful, for the duration of treatment.

The ELITONE-UUI device increases the proportion of the signal that operates at 10 Hz, intending to have a more substantial effect on UUI symptoms. Configurations are as follows:

- Configuration 1 4 seconds at 50 Hz, followed by 4 seconds at 10 Hz, followed by 6 seconds of rest, repeated.
- **Configuration 2** 6 seconds at 10 Hz followed by 6 seconds of rest, repeated. No 50 Hz stimulation is provided in this variant.

These configurations are achievable solely through software changes.

Should one or both configurations be determined to have minimal effect on the UUI, up to two additional configurations may be considered for clinical evaluation. These additional configurations include:

- Additional Configuration 3 4 seconds at 50 Hz, followed by 4 seconds at 10 Hz, followed by 6 seconds of rest, repeated for 10 minutes. Then, 6 seconds at 10 Hz followed by 6 seconds of rest, repeated for 10 minutes.
- Additional Configuration 4 Current ELITONE stimulation as defined above.

#### 6.6 Control/Sham Device

There is no control/sham group in this study

## 6.7 Regulatory Status

The ELITONE device received FDA clearance for OTC use in the treatment of female stress urinary incontinence. This study is in part designed to generate clinical data likely necessary to support FDA clearance of the proposed ELITONE-UUI device.

#### 6.8 Procurement

The electrodes, controller and all accessories are designed and manufactured by Elidah, which operates in accordance with its ISO 13485 certification for the design and manufacture of medical devices. All subjects will receive new electrodes. Subjects may be provided previously used controllers or accessories that have been inspected and confirmed to meet performance requirements. The ELITONE-UUI product is identical to the commercially available ELITONE device with the exception of the embedded software, which will be programmed and verified by Elidah prior to shipment of product to the subjects.

#### 7. SAFETY ASSESSMENTS

# 7.1 Device Safety

Elidah believes that the ELITONE-UUI device and the proposed protocol present low risk to the subjects. This assessment is supported by the following information:

- Equivalence to the ELITONE Device The only difference between the ELITONE-UUI device and the FDA cleared, commercially available ELITONE device is the embedded software that defines the stimulation waveform.
- Non-significant Risk Device Designation Electrical Neuromuscular Stimulators and Nonimplantable Electrical Incontinence Devices have been designated as non-significant risk
  devices in FDA guidance document. The ELITONE-UUI device is represented by both of
  these product types and carries the same risk profile. The device is not life-sustaining and
  failure of the device to deliver its intended therapy does not result in any notable clinical
  consequence.
- **Developed within ISO 13485 Certified Quality Management System** Elidah maintains ISO 13485 certification as a medical device manufacturer, meaning that development and production of the product adheres to accepted best practices for creating safe devices, including processes for continuous product and process improvement, reporting of complaints and adverse events, and quality control methodologies.
- Independent Device Safety Testing The ELITONE device has been tested by a third party laboratories and found to be compliant with the IEC-60601 family of standards (Medical Device Electrical Safety), including sub-standards specific to muscle stimulators and home use medical equipment. The device is also compliant with applicable IEC standards for electromagnetic compatibility.
- **Risk Mitigation by Design** As part of the product development Elidah conducts design and process risk analyses intended to identify potential device safety concerns. The development

team can then mitigate these concerns through design modifications and additional testing. Examples include:

- Risks associated with electrical shock initiating from a supply main are mitigated by preventing device operation when the device is charging (i.e. connected to an external power supply) and by minimizing the length of the provided cables.
- The device turns off automatically after 20 minutes.
- A custom cable is used, which deters an individual from using one or more of the components with another device.
- Output intensity is controlled by the user and is adjusted in ≤1mA increments, which limits the degree to which the user can be impacted by a "sudden" change in output intensity. Further, the circuit design limits the maximum current to approximately 50mA, a level consistent with commercially available EMS devices.
- Risk Mitigation by Warnings/Precautions In cases where device safety concerns cannot
  be suitably mitigated by design, user instruction is provided in the form of warnings and
  precautions. The warnings/precautions provided in the User Manual TR-1155-FORM-12)
  have additionally been baselined against the product labeling for other electrical muscle
  stimulation devices used to treat incontinence, and aligned with FDA recommendations
  regarding product labeling. For example:
  - Users are instructed not to use the device while bathing.
  - o Users are instructed not to wear the device while driving.
  - Users are instructed not to apply the device to the chest or eyes.
- Alignment with Typical Therapeutic Use This study utilizes the device in a manner that is consistent with the devices performance characteristics and with traditional therapeutic use of electrical muscle stimulators. The selection of up to 20 minutes per day and 6 weeks of treatment (6.2) was intentionally selected as being consistent with the practice of physical therapy, so as not to run the risk of overly fatiguing the pelvic floor muscles.

## 7.2 Risks and Side Effects

Participation in the study will expose the subjects to risks and side effects similar to users of electrical muscle stimulators (EMS) and transcutaneous electrical nerve stimulation (TENS) devices, both of which are low risk devices as evidenced by multiple products cleared for over-the-counter use. Note that many of the warnings and precautions associated with general use EMS and TENS devices (e.g. don't place electrodes over the eye) are less applicable to ELITONE-UUI due to the anatomic-specific nature of the ELITONE-UUI device. However, as with most medical devices, use of the product does carry health risks and potential medical side effects. Elidah does not foresee any psychological, financial, or legal risks to the subject associated with participation in the study.

The User Manual (TR-1155-FORM-12) identifies applicable warning and precautions. Each candidate receives a copy of these warnings and precautions as part of providing informed consent (see 11.2). Broadly categorized, these risks and side effects include:

- **Electrical Shock** The device delivers an electrical current to the body. Misuse of the device can result in an unintended shock which can be temporarily painful. Forms of misuse could include placing the electrode on another part of the body (e.g. across the chest) or turning the device on prior to applying the electrode to the body. The device, uses both hardware and software to control the output and has undergone extensive testing. As noted in 7.1, various safety measures are present to mitigate these risks.
- **Skin Irritation** Although the materials used in the electrode are biocompatible and used in similar, commercially available electrodes, there is a risk of skin irritation. This is likely to be

observed as persistent redness at the electrode application site, and is likely to resolve upon cessation of use.

Muscle Fatigue – The treatment is intended to exercise the pelvic floor muscles, and the
defined treatment regimen is guided by the recommended regimens of other EMS devices.
However, some subject may experience notable muscle fatigue, which, in the near-term, could
result in a temporary increase in urine leakage. Such occurrences are likely to resolve within
a matter of hours.

#### 7.3 Adverse Events and Serious Adverse Events

Adverse events are the primary means for assessing device/treatment safety. Adverse events may be identified through direct communication with the subjects and through analysis of study materials.

For all adverse events, sufficient information will be pursued and/or obtained so as to permit (1) an adequate determination of the outcome of the events (i.e., whether the effect should be classified as a serious adverse effect) and (2) an assessment of the causal relationship between the adverse event and the device/treatment.

Adverse events determined to be associated with the device/treatment will be followed until they are resolved or stabilized. The CTCAE definitions and scoring of Adverse Events will be used.

An **adverse event (AE)** is generally defined as any unfavorable and unintended symptom or finding which either occurs during the study, having been absent at baseline, or, if present at baseline, appears to worsen during the study. Adverse events are recorded regardless of their relationship to the study intervention.

A **serious adverse event (SAE)** is generally defined as any adverse event that results in death, is life threatening, requires inpatient hospitalization or prolongation of existing hospitalization, results in persistent or significant disability/incapacity, or is a congenital anomaly: Grades 3-5.

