## 2.2 Primary Endpoint

Treatment efficacy is assessed by comparing the average number of urinary incontinence episodes per day at the end of treatment to the corresponding pre-treatment number.

Safety is determined by review of Adverse Events as defined in 7.3, and determination of no serious adverse event during the study.

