## 7.4 Reporting Procedures

Subjects are instructed to report adverse events at the time of occurrence via either phone or email. Adverse events may also be identified during routine communication with the subject or review of the subject's Daily Log.

The Data Safety and Monitoring Board will use the following 0 to 5 scale to grade adverse events (AE): 0 = none or event is not clinically significant, 1 = mild AE that does not require treatment, 2 = moderate AE that does require treatment, but resolves completely, 3 = severe AE (e.g. one that results in temporary inability to conduct one or more everyday activities and requires ongoing medical attention), 4 = life threatening or results in permanent inability to conduct one or more everyday activities, and 5 = death.

In the event of an AE rated ≥2 the Clinical Director will instruct the subject to obtain medical treatment from a qualified healthcare professional. If the subject becomes ill or is physically injured due to the use of the ELITONE-UUI device, she will not be responsible for the costs required to diagnose or treat such injury. The costs of diagnosis and medical care for any complication, injury, or illness caused by the study device or properly performed non-standard of care investigational procedure required by the study will be covered by Elidah, as long as the subject has followed the study protocol. The subject will not lose any of her legal rights and she does not release Elidah and the study staff from liability for mistakes or intentional misconduct by participating in the study.

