## 9.4 Interim Analyses and Stopping Rules

Due to the short duration of the study (6 weeks) and likely rapid enrollment (1 month), there are no plans for an interim analysis.

In the event of a serious adverse event related to the device/treatment the study will be halted until the safety issue can be addressed (see 7). Due to the small enrollment size, a pre-specified number of adverse events will not be used to trigger an early end to the study.

\_

<sup>2 Richardson et al, "Pelvic floor electrical stimulation: A comparison of daily and every-other-day therapy for genuine urge incontinence", Adult Urology, 48(1):110-118, 1996.

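### Section 7.3 ties its outcome-based definition of a serious adverse event to severity grades 3 to 5, and the grading scale in 7.4 does not line up with that list

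*Combined protocol and SAP*

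**What the plan says.** Section 7.3 defines a serious adverse event first by death and threat to life, and then by the remaining outcomes, ending in a grade range: "requires inpatient hospitalization or prolongation of existing hospitalization, results in persistent or significant disability/incapacity, or is a congenital anomaly: Grades 3-5". The same section states: "The CTCAE definitions and scoring of Adverse Events will be used". It also says: "Adverse events are recorded regardless of their relationship to the study intervention".

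Section 7.4 prints a 0 to 5 scale and tells the Data Safety and Monitoring Board to grade with it. Two steps matter here. The first is "2 = moderate AE that does require treatment, but resolves completely". The second is "3 = severe AE (e.g. one that results in temporary inability to conduct one or more everyday activities and requires ongoing medical attention". Grade 4 covers threat to life or a permanent inability, and grade 5 is death. The scale is not described as CTCAE.

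Serious status is used in two places. Section 2.2 makes it part of the primary endpoint: "Safety is determined by review of Adverse Events as defined in 7.3, and determination of no serious adverse event during the study". Section 9.4 uses it to pause the trial: "In the event of a serious adverse event related to the device/treatment the study will be halted until the safety issue can be addressed".

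**The concern.** Seriousness describes what an event led to; severity describes how intense it was. Section 7.3 treats them as one thing by closing an outcome list with a grade range. If the list and the range always selected the same events, this would do no harm. They need not do so on the 7.4 scale, and 7.3 points to a second scoring system without saying which one the range refers to.

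What is at stake is the reported safety conclusion and the halt. Section 2.2 relies on there being no serious event and sets no condition on relatedness, so one classification can change whether that criterion is met. The choice would be made after the event is known. Under 10.5 the board includes, at a minimum, the Clinical Director and a person responsible for the device's technology, alongside someone with relevant medical training. Section 6.7 says the data are meant in part to support FDA clearance, so the conclusion will be relied on outside the study.

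**Working it through.** No arithmetic applies. The check sets the 7.3 list against the 7.4 scale in both directions and then follows two example events through 2.2 and 9.4.

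**From list to scale**

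| Outcome in 7.3 | Place on the 7.4 scale |
|---|---|
| Death | Grade 5 |
| Threat to life | Grade 4 |
| Lasting or significant disability | Grade 4 if permanent; otherwise not clearly placed |
| Hospital admission or longer stay | Named in no grade; 2 or 3 by judgement unless life threatening |
| Congenital anomaly | Named in no grade |

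The point rests on the hospitalization row. Grade 2 requires that the event be moderate, need treatment and resolve fully. It puts no limit on where the treatment is given.

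**From scale to list**

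| Grade in 7.4 | Listed outcome in 7.3 |
|---|---|
| 2 | May meet hospitalization |
| 3 | May meet none, unless the patient is admitted or the incapacity is judged significant |
| 4 | Meets threat to life or disability |
| 5 | Meets death |

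**Two events followed through**

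- *Event A: moderate, short admission, full recovery.* By the list it is serious. If graded 2, it falls outside grades 3 to 5; if graded 3, it falls inside. On the first classification the 2.2 criterion fails and, if the event is related, 9.4 halts the study. If a grade of 2 is taken to govern, the criterion still holds and there is no halt.
- *Event B: severe, a temporary loss of some daily function, continuing outpatient care.* By grade it is serious. By the list it may not be. The consequences run the other way.

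**Which scale.** Section 7.3 names CTCAE, and 7.4 prints the scale the board is to apply. The documents do not reproduce the CTCAE grades, so whether the two systems would agree on a given event cannot be checked here. The text leaves open which of them the range of 3 to 5 refers to.

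**Which rule prevails.** Neither 7.3, 7.4, 2.2 nor 9.4 says what happens when outcome and grade disagree. Section 7.3 asks for enough information to decide whether an event is serious, but gives no tie-break.

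**What does not depend on this.** Under 7.4 and 7.5, referral to medical care and follow-up by the Clinical Director start at grade 2, so Event A would be referred and followed on either classification.

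**The case against.** The strongest reply is that the grade range is a gloss on the list: events with these outcomes are to be placed in grades 3 to 5. On that reading an admitted patient is graded at least 3 and nothing conflicts. The 7.4 wording also allows it. Grade 2 is confined to moderate events, the grade 3 description is only an example, and an inpatient is usually unable to carry out some daily activities. This stands to the extent that a grade of 2 for a hospitalized event is possible, not forced. It does not remove the problem, because nothing in 7.4 tells the board to raise the grade of an admitted patient. Nor does the gloss settle Event B, where the grade is 3 and the outcome may be absent.

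A second reply is that 7.3 allows temporary incapacity to count if it is significant. That is fair, and it makes the second direction the softer of the two.

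A third is that the device is low risk and that 3.2 reports earlier ELITONE trials without serious adverse events. That is also true. It bears on how often the ambiguity would bite, which the documents do not quantify.

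A reader might go further and infer that one unrelated hospital stay settles the safety verdict by itself. The documents do not support that. Section 2.2 also calls for review of all adverse events, 7.3 requires a causality assessment, and 9.5 contains no formal safety success rule.

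**Conclusion.** Wrong as written. Section 7.3 merges seriousness with severity and leaves the scale unidentified. For two kinds of event the protocol can therefore give two answers: a moderate hospitalized event that resolves, and a severe event managed without a listed outcome. Classification of such an event is left to the board's discretion after it has occurred.

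The size is best stated as a consequence. One event classified one way or the other can change whether the no-serious-event part of 2.2 is met and, if it is related, whether the study halts. No probability can be attached. An interval around zero or one event among 40 participants would describe any single event in a study of this size and would not measure this defect.

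A reader might also infer that the 7.4 scale has no room for two of the five listed outcomes. That overstates the case. A severity scale need not name outcomes, grade 3 is open-ended, and congenital anomaly carries little weight because 4.2 excludes women who are or may be pregnant or are trying to conceive.

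The conclusion assumes only that the board applies the printed 7.4 wording and that no separate classification rule exists outside the documents.

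**What to change.** In 7.3, delete the grade range and state that a serious adverse event is any adverse event meeting a listed outcome, whatever its severity grade. Record severity as a separate item on one named scale, used in both 7.3 and 7.4. In 9.4, halt for any related serious adverse event or any related event of grade 3 or higher. The 9.4 change is needed because deleting the range alone would let a related grade 3 event without a listed outcome escape the halt. Section 2.2 already points to 7.3 and would pick up the new definition.

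The cost is a wording amendment with IRB review and no new assessments for participants. The downside is that grade 3 events without a listed outcome would be reported by grade and not counted as serious in the 2.2 endpoint. Defining a serious event as any listed outcome or any event of grade 3 to 5 would avoid that and also remove the ambiguity, but it would keep severity mixed into the definition of seriousness.
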